## 4.2.2 Exclusion Criteria

Mothers who meet any of the criteria specified in [Section 4.1.2](#) will be excluded from this component.

## 4.2.3 Step 2 Inclusion Criteria: Cohort 2 only

Cohort 2 maternal participants who subsequently choose to initiate PrEP complete Step Change Visits 1 and 2, refer to [Section 6.2.3.2](#) and [Appendix IIB](#) and must meet all of the following criteria in order to enter Cohort 2/Step 2 to initiate PrEP:

**4.2.3.1** HIV negative by HIV RNA testing at Step Change Visit 1 and HIV rapid test negative and absence of symptoms of acute HIV infection (i.e. acute viral illness). at Step Change Visit 2.

- 4.2.3.2** Prior to entering Step 2, Hepatitis B negative by Hepatitis B surface antigen test performed at Step Change Visit 1.
- 4.2.3.3** Normal ( $\geq 90\text{mL/min}$ ) estimated creatinine clearance (CrCl; Cockcroft-Gault formula) at previous assessment and negative or trace proteinuria (less than Grade 1) at Step Change Visit 1.
- 4.2.3.4** Willing to take PrEP up to 26 weeks postpartum.
- 4.2.3.5** Regular access to a cellular phone that is able to receive and send SMS messages.

#### **4.3 Infant Enrollment**

Infants enter the study at the same time their mother is enrolled. Infants in the PK Component - Group 1 and the PrEP Comparison Component enter the study, *in utero*, and infants in the PK Component - Group 2 enter the study six to 12 weeks after birth. There are no set inclusion or exclusion criteria for infants. If an infant is deemed too ill to undergo study procedures, the Site Investigator may opt to omit specific study procedures and prioritize those necessary for clinical management.

#### **4.4 Co-Enrollment Considerations**

Maternal and infant participants should not take part in any concurrent research studies that use drugs or medical devices while in follow up. Co-enrollment in observational or other studies may be allowable with approval in advance by the Protocol Teams of both studies. Requests for such approval should be emailed to the CMC.

#### **4.5 Recruitment, Screening, and Enrollment Process**

Sites will be responsible for developing appropriate recruitment processes that are geared toward their respective local communities. Recruitment materials should undergo approval, if applicable, per institutional review board (IRB)/Ethics Committee (EC) policies and procedures.

Women at heightened risk of HIV acquisition will be recruited for the PK Component and PrEP Comparison Component from public health centers where standard of care HIV pre- and post-test counseling procedures include a standardized HIV risk assessment. Study staff will approach women who, based on this risk assessment, perceive themselves to be at heightened risk and express interest in learning more about methods to protect themselves. After introducing the study, study staff will invite women who express potential interest in the study to initiate the informed consent process; those who provide informed consent will then initiate the study screening process. Women who do not express potential interest in the study will be referred to standard of care HIV prevention services.

All sites are eligible to participate in the PK Component; however, some may elect to opt out. It is also possible that not all sites will be needed to reach full accrual for this component. It is anticipated that all sites will participate in the PrEP Comparison Component.

The IMPAACT Data Management Center (DMC) Subject Enrollment System (SES) will be used to assist with tracking the screening and enrollment process for both the PK Component and PrEP

Comparison Component. When informed consent is obtained, participant identification numbers (PIDs) will be assigned to the mother and infant and a study-specific screening number will be obtained for the mother-infant pair through the SES. For pairs found to be eligible, enrollment will occur upon successful entry of required eligibility data into the SES. For pairs who are found to be ineligible for the study, or who do not enroll in the study for any reason, an eCRF will be entered to record the screening outcome. Refer to [Section 9.3](#) for more information on monitoring participant accrual in this study.

#### **4.6 Participant Retention**

Once a participant is enrolled in this study, the study staff will make every effort to retain them for the expected duration of follow-up in order to maximize statistical power and minimize potential bias associated with loss-to-follow-up. Study staff are responsible for developing and implementing local procedures to reach this goal. Refer to [Section 9.3.1](#) for more information on monitoring participant retention in this study.

#### **4.7 Participant Withdrawal or Termination from the Study**

Regardless of the participant retention methods used, maternal participants may voluntarily withdraw from the study for any reason at any time. The site IoR or designee also may withdraw participants from the study to protect their safety and/or if they are unwilling or unable to comply with required study procedures.

Participants may also be withdrawn/discontinued from the study by the site investigator or designee under the following circumstances:

- Participant re-locates away from access to any study site or is otherwise determined by the study staff to be lost-to-follow-up and unlikely to return to the study.
- Participant judged by the investigator or designee that continued participation in the study would be unsafe or otherwise not in the best interest of the participant, after consultation with the Protocol Team.
- Participant fails to comply with the study requirements so as to cause harm to him/herself or to seriously interfere with the validity of the study results.
- At the discretion of the IMPAACT leadership, NIAID, NICHD, the Office for Human Research Protections (OHRP), the U.S. FDA, the pharmaceutical supplier(s), an in-country national health or regulatory agency, or the IRB/EC.

Every reasonable effort will be made to complete final evaluations for participants who terminate from the study prior to the last study assessment or visit; study staff will record the reason(s) for all withdrawals from the study in the participants' study records.

For any participant who is withdrawn from the study prior to scheduled completion of follow-up, study staff will document the reason for the withdrawal in detail and will make every effort to complete final evaluations as described in [Section 6.4](#). If the circumstances that led to a participant's withdrawal change (e.g., she returns to the study site area after having re-located previously), the site investigator or designee should contact the Protocol Team to discuss options for resumption of follow-up.

## 5 STUDY DRUG CONSIDERATIONS

Site pharmacists should consult the *Pharmacy Guidelines and Instructions for DAIDS Clinical Trials Networks* for standard pharmacy operations.

Study drug is defined for this study as FTC/TDF 200 mg/300 mg (Truvada®). Truvada® is approved by the U.S. Food and Drug Administration (FDA) for the treatment of HIV-1 infection and for PrEP to reduce the risk of sexually acquired HIV in adults at substantial risk. Further information on Truvada is available in the current package insert available at: <https://rsc.niaid.nih.gov/clinical-research-sites/pi-list>

Maternal participants in this study may be exposed to study drug through direct ingestion; infants may be exposed to study drug *in utero* and through breastfeeding.

### 5.1 Study Drug Regimen

Maternal participants in Group 1 and Group 2 of the PK Component, in Cohort 1 of the PrEP Comparison Component, and Cohort 2/Step 2 of the PrEP Comparison Component will receive a fixed dose combination of FTC/TDF 200 mg/300 mg to be taken by mouth once daily for the duration specified in [Section 5.1.2](#).

#### 5.1.1 Study Drug Administration

FTC/TDF will be administered orally as one fixed dose oral combination tablet (FTC 200 mg/TDF 300 mg) once daily, with or without food. In the PK Component, administration will be directly observed. Instructions for maternal participants in the event of vomiting relevant for both components are below. Further guidelines for study drug administration in the PK Component and PrEP Comparison Component are specified in [Sections 5.1.1.1](#) and [5.1.1.2](#), respectively.

In the event of vomiting, maternal participants in both the PK and PrEP Comparison Components, will be instructed by study staff as follows:

- If the maternal participant vomits within 15 minutes after taking a tablet, and suspects that the tablet has been thrown up (i.e., the tablet is visible in the vomit), she should wait approximately 30 minutes and then take another FTC/TDF tablet.

Note: Participants in the PK Component should notify staff immediately upon vomiting and the same DOT procedures described below should be followed for the additional tablet.

- If this maternal participant vomits again after taking the second tablet, she should not take any more tablets that day, but try again to take a tablet at her daily dose time the next day.
- If the maternal participant is not able to determine that the tablet has been thrown up (i.e., the tablet is not visible in the vomit), she should not take any more tablets that day, but try again to take a tablet at her daily dose time the next day.

### **5.1.1.1 PK Component**

In the PK Component, study staff must monitor maternal participants' daily administration of FTC/TDF. Each study site must establish standard operating procedures (SOPs) describing how this will be done; depending on site-specific feasibility, options may include:

- Directly observed therapy (DOT) at the study site
- DOT at the participant's home or other community-based location (see also [Section 6.1.1](#))
- Real-time video-based DOT (e.g., live streaming via FaceTime, Tango, Skype, or other similar method)

The first two options listed above, which involve in-person direct observation by study staff, are preferred and should be used whenever possible. When use of these options is not possible, the third option of observation via live streaming video should be used. If live streaming is not possible, a video file may be saved by the participant and sent to study staff for non-live viewing, provided the file is dated and time-stamped.

In the expected rare event that one of the three options listed above cannot be used, participants will be contacted to self-report their daily dose administration via telephone call or audio message, text message, and/or still photo. Whether directly observed or self-reported, all types of documented dose administrations will be adequately source documented and entered into electronic case report forms (eCRFs); however, dose administrations that are not directly observed will not be considered in primary analyses.

### **5.1.1.2 PrEP Comparison Component**

In the PrEP Comparison Component, maternal participants will be encouraged to select a consistent daily "dose-time;" however, if a maternal participant forgets to take a dose at that time, the dose may be taken later in the day, as long as only one dose is taken on any calendar day.

## **5.1.2 Study Drug Duration**

### **5.1.2.1 PK Component**

Maternal participants in Group 1 and Group 2 of the PK Component will take FTC/TDF for 12 weeks, beginning on the day of enrollment and continuing through the day of the Week 12 visit. Participants who have not delivered by their Week 12 visit may elect to continue PrEP thereafter through their labor and delivery visit.

### **5.1.2.2 PrEP Comparison Component**

Maternal participants in Cohort 1 of the PrEP Comparison Component will take FTC/TDF through pregnancy and for 26 weeks postpartum, beginning on the day of enrollment and continuing through the day of the Week 26 postpartum visit.

Maternal participants in Cohort 2 of the PrEP Comparison Component who declined PrEP initiation during pregnancy will not take FTC/TDF for the duration of the study unless they undergo a step change and enter Cohort 2/Step 2.

Maternal participants in Cohort 2/Step 2 of the PrEP Comparison Component will take FTC/TDF for a variable duration, depending on timing of Step 2 entry. The duration will begin on the day of enrollment in Step 2 and continuing through the day of the Week 26 postpartum visit.

## **5.2 Study Drug Formulation**

FTC/TDF (supplied for this study as Truvada®) is a fixed dose combination tablet containing 200 mg of emtricitabine (FTC) and 300 mg of tenofovir disoproxil fumarate (TDF) in each tablet.

Tablets must be stored in their original containers at 25°C (77°F); with excursions permitted to 15-30°C (59°-86°F) (see USP Controlled Room Temperature). Each container is packaged with a child-resistant screw cap and contains a silica gel to protect the product from humidity. The silica gel should not be removed from the container.

### **5.2.1 Study Drug Supply**

FTC/TDF will be supplied by Gilead Sciences, Inc. and made available to study sites through the National Institute of Allergy and Infectious Disease (NIAID) Clinical Research Products Management Center (CRPMC). Upon successful completion of protocol registration procedures, study drug may be obtained by the site pharmacist following instructions provided in the *Pharmacy Guidelines and Instructions for DAIDS Clinical Trial Networks*.

### **5.2.2 Study Drug Accountability**

Site pharmacists must maintain complete records of all study drugs received from the CRPMC and subsequently dispensed.

The site pharmacist must follow the instructions in the Pharmacy Guidelines and Instructions for DAIDS Clinical Trials Networks for the destructions of unused study products.

## **5.3 Behavioral Counseling and Adherence Support**

### **5.3.1 PK Component**

Adequate study drug adherence is required from maternal participants in the PK Component to accurately establish the target TFV-DP levels in DBS for use in the PrEP Comparison Component. To support near perfect dosing in the PK Component, study teams will have daily contact with maternal participants and directly observe each dose, providing counseling as directed by the circumstances. The mechanism for achieving this may differ by site and over time, being laid out in a standard operating procedures document. At in-clinic planned study visits, adherence and sexual health protection counseling will be offered as detailed below.

Adherence and Sexual Health Protection Counseling:

*Integrated Next Step Counseling (iNSC, described in Section 5.3.2)* will be adapted for context of PK Component. All maternal participants in both groups are provided education, support and problem solving at time of observed dose by the team member observing the dose (in person or virtually). Added efforts to engage participants failing to come-in, be present at home when a home visit has been scheduled, or call-in for observation of dose taking will include exploration of factors that could facilitate near-perfect/perfect coverage of observation. At study visits,

women will be asked to engage in brief, discussions about their current strategies for sexual health protection and experiences with DOT. For women engaging well with DOT, support is provided to maintain this success. For women engaging intermittently or insufficiently with DOT, discussions will focus on problem solving and targeting increased DOT engagement and high adherence regardless of DOT. Thus, the iNSC approach will be used to promote non-PrEP related sexual health protection and support participants in their engagement with DOT and adherence.

### 5.3.2 PrEP Comparison Component

#### Adherence and Sexual Health Protection Counseling:

*Integrated Next Step Counseling (iNSC).* At study visits, all maternal participants in both cohorts receive iNSC, a participant-focused discussion of sexual health and well-being during the delivery of HIV-negative test results. iNSC includes exploration, problem solving and skills building around non-biomedical strategies to prevent HIV and other STIs and general well-being for all participants. For those receiving PrEP (Cohort 1 or Cohort 2/Step 2), counselors assess maternal participants' desire to remain on PrEP. With confirmation of desire to continue with PrEP it subsequently focuses on a discussion of PrEP adherence. For those not on PrEP, the discussion ends with a discussion on whether she is interested in starting PrEP and providing appropriate follow-up, accordingly. For those who have been prescribed PrEP but have yet to start taking it, the discussion focuses on her decision to start PrEP and on regimen adherence education and planning. iNSC is participant-focused, relies on participant experiences rather than self-reported performance (e.g., does not ask participants to report numbers of missed doses or number of occurrences of condomless sex, but rather asks about experiences [positive and negative] with sexual health protection, areas where the participant would like to feel more confident, skilled or comfortable), uses Motivational Interviewing and problem solving strategies, and is based on a situated information, motivation and behavioral skills model of sexual health protection (which contextualizes individual behavior within its social-cultural and structural context).

*Drug level monitoring with feedback.* DBS samples to measure TFV-DP levels will be obtained from participants in Cohort 1 and Cohort 2/Step 2 as per [Appendix IIA](#). DBS levels strongly correlate with PrEP efficacy, so users and clinicians can interpret the drug level in the context of HIV prevention. TFV-DP levels in red blood cells (measured with DBS), by virtue of a 17-day half-life, represent cumulative adherence rather than only recent adherence. Monitoring outcomes of preventive medications with biological measurements is common in the management of chronic diseases. Per drug thresholds, established in the PK Component, specific ranges will be defined for a minimum three adherence categories, aligned with other similar studies and will be used to provide guidance for adherence counseling. (e.g. below adequate, adequate and above adequate). All participants in Cohort 1 and Cohort 2/Step 2 will receive iNSC with drug level feedback based on this categorization.

Participants will be contacted when their DBS TFV-DP concentration results become available to site staff. Targeted iNSC, an adapted version of the standard PrEP check-in used at each visit (iNSC), will be used in delivering results of drug testing to participants. The approach allows staff to share results with participants in a systematic manner and differs based on result being delivered. Discussions around adherence and sexual health protection are offered (as an option for those with optimal levels) or requested as part of study procedures (for sub-optimal levels) to participants. Based on current evidence, any concentration below excellent will be considered below adequate. This threshold will be updated as needed should evidence emerge suggesting that women can achieve high protection with lower concentrations. Detailed steps for these

procedures are provided in the study-specific iNSC manual/workbook and associated training material.

During the PrEP Comparison Component, completion of iNSC sessions will be documented via eCRF. Counselors will complete a tracking form at the end of each session documenting the specific elements of iNSC included or deferred and related details.

#### SMS Support:

Beginning with enrollment and continuing through follow-up, all maternal participants, regardless of cohort, will receive periodic informational one-way messages about pregnancy and infant care. Message content and frequency, as well as standardized procedures for delivering messages via an automated computer system will be described in the study-specific MOP.

Maternal participants in Cohort 1 and Cohort 2/Step 2 will also receive weekly two-way text messages that provide general adherence support. Beginning the week following enrollment (participants in Cohort 1), or the week following Step Change Visit 2 (participants in Cohort 2/Step 2), and continuing through follow-up, each week, participants will receive a text message reminding them about the study support and inquiring how they are doing (e.g. ‘are you ok?’). Participants will be instructed to respond within 48 hours either that they are doing well or that they have a problem and request assistance. A study staff member will call to follow-up with any participant whose response indicates that there is a problem, and participants who fail to respond within two business days. Site staff will be expected to respond to text messages only during regular clinic hours, but are not restricted to do so. Participants will be instructed that all emergencies should be handled through their usual means such as contacting the nearest hospital emergency department. Message content and standardized procedures for delivering messages and tracking responses for two-way messaging via an automated computer system will be described in the study-specific MOP.

Delivery of the SMS support package will be documented via usage statistics and automated system reporting of message delivery data. Telephone and in-person follow-up will be tracked manually and source documented.

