#### 6.2.3.1 Maternal Participants in Cohort 1 Who Subsequently Stop PrEP

To the extent possible, staff should try to identify the reasons for maternal participants choosing to stop PrEP. Once the maternal participant has stated that she is not willing to continue PrEP and the decision to stop PrEP will be entered into an eCRF. If not already required for the study visit at which this decision is made, the following additional study procedures should be conducted:

- iNSC
- TFV-DP level (DBS)
- HIV RNA test

This will not constitute a change from Cohort 1 to 2; the maternal participant will continue to be followed as per her original assignment per [Appendix IIA](#) with the exception of the following evaluations:

- iNSC with drug level feedback

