### **6.3.3 Maternal HIV Seroconversion: Management of Maternal Participants at Every Visit (PrEP Comparison Cohort only)**

Maternal participants in the PrEP Comparison Component with confirmed HIV infection will remain on-study and continue to be followed through scheduled study exit per the applicable SoE ([Appendix IIA](#) or [IIB](#)). However, because they will no longer be on PrEP, the following procedures will no longer be performed among these participants:

- Rapid HIV test
- Study drug dispensing
- iNSC with drug level feedback
- Two-way SMS support (one-way SMS support should continue)
- PrEP acceptability assessment
- TFV-DP (DBS) level

In addition, ALT, creatinine, CrCl and HIV RNA testing will be performed at a decreased frequency—approximately every six months during scheduled study visits—to monitor chemistries and HIV viral load among these participants.

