## **6.5 PrEP Comparison Component – Interim Visit for Drug Level Feedback**

Study staff will contact maternal participants within three business days of site receipt of their DBS TFV-DP concentration results. Delivery of test results will follow the approach detailed in [Section 5.3.2](#) and the study-specific iNSC manual/workbook and associated training material. Drug level feedback should be scheduled to take place as soon as possible after receipt of the PK result. If an interim visit cannot be scheduled in-person, the visit may take place over the phone.

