## **7.3 Expedited Adverse Event (EAE) Reporting**

EAEs will be reported only for participants in this study who are exposed to study drug.

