Incidence rate ratio (among PrEP exposed vs. PrEP unexposed women) of cumulative adverse events up to 26 weeks postpartum	Incidence rate ratio of cumulative AEs up to the week-26 postpartum visit (among PrEP exposed vs. PrEP unexposed women) estimated based on Poisson distribution (with 95% Wald CI).

Supplemental Analyses:

- Analyses will be repeated stratified by time period (i.e., antepartum (AP) and postpartum (PP), and within AP stratified by gestational age category of enrollment).
- Rates of maternal adverse events in AP and PP periods will also be calculated and compared across levels of PrEP adherence (based on TFV-DP levels in dried blood spots). Models will be fit adjusting for potential confounders.

- To compare time to first adverse event in PrEP exposed vs. PrEP unexposed women, the hazard ratio (95% CI) will be estimated with Logrank test p-value from Cox proportional hazards regression on time to first AE with PrEP exposure as a time-varying covariate.

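### Unscheduled contact is heavier in PrEP-exposed time, so clinical Grade 3 or higher AEs may be detected somewhat more completely there, and the SAP rate ratios have no safeguard

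*Protocol*

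**What the plan says.** **Same in both cohorts.** Protocol 6.2.1.2 to 6.2.1.7 and Appendices IIA and IIB give both cohorts the same follow-up visits. History since the last visit and AE review take place at each of them, and ALT and creatinine are drawn at the same time points. Protocol 7.2 applies the AE definition from enrollment whatever the exposure. Under 7.2.1 and 7.2.2, Grade 2 or higher AEs and all SAEs go on the AE eCRF for both cohorts, with some differences in detail between mothers and infants.

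**Different by cohort.** Protocol 5.3.2 (SMS Support) says: "Maternal participants in Cohort 1 and Cohort 2/Step 2 will also receive weekly two-way text messages that provide general adherence support". The message asks how the woman is doing. "A study staff member will call to follow-up with any participant whose response indicates that there is a problem", and also with anyone who has not replied within two business days. Women not on PrEP receive one-way informational messages only. Protocol 6.5 adds: "Study staff will contact maternal participants within three business days of site receipt of their DBS TFV-DP concentration results". Protocol 7.3 limits expedited reporting: "EAEs will be reported only for participants in this study who are exposed to study drug".

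**How long it lasts.** The texts start the week after enrollment or Step Change Visit 2, "and continuing through follow-up, each week, participants will receive a text message reminding them about the study support". For a Cohort 1 woman who stops PrEP, 6.2.3.1 says "the maternal participant will continue to be followed as per her original assignment per" Appendix IIA; only the counseling with drug-level feedback is dropped. After confirmed HIV infection, 6.3.3 lists among the discontinued procedures "Two-way SMS support (one-way SMS support should continue").

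**Analysis.** SAP 6.3.2 specifies: "Incidence rate ratio of cumulative AEs up to the week-26 postpartum visit (among PrEP exposed vs. PrEP unexposed women"), from a Poisson model with a Wald interval. Exposed person-time starts at study entry for Cohort 1 and at Step 2 entry for Cohort 2. Stopping PrEP is handled by treatment policy. SAP 6.3.4 does the same for infants.

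**The concern.** The outcome is not confined to events found at scheduled visits. Protocol 8.1 covers every AE identified in the study, and 7.2.1 takes in laboratory results whether the test was scheduled or ordered for clinical reasons. A problem raised in a text or call-back, or a test that it prompts, can therefore become a primary-outcome event. A woman not on PrEP has no such prompt between visits. Her clinical events depend mainly on interval history, which Protocol 6.8 allows to rest on self-report and which spans up to 12 weeks (AP Week 12 to 24, AP Week 24 to 36, PP Week 14 to 26).

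Because stopping PrEP does not end exposed time in the SAP and does not end the texts, the extra contact closely tracks the exposed side of the contrast. For a Cohort 2 switcher it begins about when her time changes from unexposed to exposed. The study is open label, and SAP 2.2.2 hypothesizes higher AE rates with PrEP, which is the direction that fuller detection would push. Protocol 9.2.1 discusses confounding and limited power but not unequal detection.

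**Working it through.** **1. The plan's nearest figure.** Neither document quantifies detection. The closest stated number is the worked example in Protocol Table 10: 10% of 100 against 23% of 200, two-sided alpha 0.05, 80% power.
- Pooled proportion = (200×0.23 + 100×0.10)/300 = 0.1867
- Null SE = √(0.1867×0.8133×(1/200+1/100)) = 0.0477
- Alternative SE = √(0.23×0.77/200 + 0.10×0.90/100) = 0.0423
- Power = Φ((0.13 − 1.96×0.0477)/0.0423) = 80.6%

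The figure reproduces, and it confirms that the design targets large differences.

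**2. Contacts.** Take a woman enrolled at 24 weeks and delivering at 40 (illustrative).
- Follow-up = (40−24)+26 = 42 weeks
- Scheduled follow-up visits in either cohort: AP 4, 8, 12, L&D, PP 6, 14, 26 = 7
- Exposed women also have about 41 weekly texts and up to 6 drug-level contacts
- Ratio of all contacts = (7+41)/7 = 6.9, or (7+41+6)/7 = 7.7 with drug-level contacts
- Ratio of scheduled AE reviews = 7/7 = 1; ratio of scheduled ALT/creatinine draws = 1

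The imbalance lies wholly in unscheduled contact.

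**3. Effect on the ratio.** Observed ratio = true ratio × (share detected in exposed time / share detected in unexposed time). Set the true ratio to 1 and detection in exposed time to 100%. The unexposed share *c* is an assumption; the documents give none. The middle column shows the dilution if half of all counted events were scheduled chemistry results detected equally (also an assumption): 1/(0.5+0.5*c*). The last column is a simulation with 200 and 100 units of person-time, following the 2:1 target, and 0.2 events truly occurring per unit in both groups. It gives the chance that the lower 95% Wald limit exceeds 1 when every counted event is clinical.

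| *c* | Ratio, clinical events (1/*c*) | Ratio, all events if half are chemistry | Chance of a false harm finding |
|---|---|---|---|
| 1.00 | 1.00 | 1.00 | 2.0% |
| 0.95 | 1.05 | 1.03 | 3.3% |
| 0.90 | 1.11 | 1.05 | 4.6% |
| 0.80 | 1.25 | 1.11 | 9.9% |

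**4. Against sampling error.** With the same person-time and unexposed rate *r*, the smallest ratio *m* detectable with 80% power solves Φ(ln *m* / √(1/(100*r*) + 1/(200*rm*)) − 1.96) = 0.80. This gives about 2.6, 2.0 and 1.8 at *r* = 0.1, 0.2 and 0.3. At *r* = 0.2, an observed 1.25 has SE(log ratio) = √(1/20+1/50) = 0.265 and a 95% interval of 0.74 to 2.10. A detection effect in the assumed range would usually sit inside the interval. It would still shift the estimate and both limits upwards.

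**The case against.** Several points on the other side stand.

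- Contact is not AE ascertainment. The texts are adherence support, no AE questions are specified, and women are told to take emergencies to usual care. The interim-visit column of Appendix IIA lists counseling only. A reader might infer from the roughly sevenfold contact ratio that AEs are sought several times as often in exposed time. The documents do not support that, because scheduled ascertainment is one to one.
- A reader might infer that the extra contact runs only while women take PrEP. It does not: the texts continue after stopping, while drug-level feedback counseling ends.
- Expedited reporting might look like a second source of outcomes for exposed women. It is a reporting route for events the site already knows, and SAEs in both cohorts go on the eCRF. What remains is the DAERS reconciliation in SAP Attachment 1, which can recover omitted events in exposed participants only. That is a small residue.
- Grade 3 or higher events are those that interval history is least likely to miss. Call-backs could also bring earlier care and fewer severe events.
- Infant visits and creatinine time points are identical in both cohorts, and the weekly text asks about the mother.

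Two replies carry less weight. SAP 6.3.2 and 6.3.4 plan comparisons across TFV-DP levels. These largely hold texting constant among PrEP users, but they are supplementary and do not address exposed against unexposed. The SAP also lists the support package within the treatment; yet the objective is the safety of FTC/TDF, and better detection by text message is not a drug effect.

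**Conclusion.** The concern holds in a limited form. Unscheduled contact is unequal in a way that closely tracks SAP exposed time, events found through it can count, and the SAP neither records how an AE was found nor tests whether that matters. The plausible result is modest over-detection of clinical Grade 3 or higher maternal AEs in exposed time, with a smaller effect for infants and little for scheduled chemistry.

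The direction towards harm is likely but not shown. The range of 1.05 to 1.25 rests on an assumed 5% to 20% shortfall in unexposed capture and full capture in exposed time, and it applies to clinical events only. It should not be read as an estimate of the bias, and the documents do not support a claim that the primary ratios will show false harm.

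**What to change.** - **AE eCRF:** add one field for how the event first came to notice: scheduled visit, scheduled laboratory test, SMS/phone/interim contact, or EAE reconciliation. Protocol 5.3.2 already requires telephone and in-person SMS follow-up to be tracked and source documented, so those records can help fill it.
- **SAP 6.3.2 and 6.3.4:** add a sensitivity rate ratio limited to events whose detection depends little on extra contact. These are scheduled laboratory abnormalities, deaths, and SAEs on the AE eCRF not first found through SMS, phone or interim contact or DAERS reconciliation. Report clinical and chemistry events separately.
- **Before database lock:** check SAEs against source in both cohorts, not only through DAERS reconciliation.
- **Interpretation:** state that a clinical-AE excess not seen in the restricted ratio may partly reflect detection. Do not commit in advance to not attributing it to PrEP. The restricted ratio covers different and fewer events, and such a rule could dismiss a real excess of non-serious Grade 3 symptoms.

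The cost is one eCRF field, one additional analysis for each AE estimand and a wider source check. The restricted ratio will have fewer events and a wider interval, so it can inform interpretation but not settle it.
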